## **6. INFORMED CONSENT AND DATA PROTECTION**

[figure not shown]
### **6.1 Informed Consent**

This study is an observational and retrospective analysis, therefore it does not provide direct involvement of patients (see the AIFA Guidelines for Observational Studies, Determination 20/03/08 - CURI No. 76 of 31/03/2008). Since collected data will be anonymous, they are not subject to Privacy Code regarding the protection of personal data. Data will be collected exclusively from regional administrative databases. To respect privacy, regional institution anonymised all data that is sent monthly by regional hospitals. Anonymization is carried out by constructing a unique code to replace the patient's fiscal code. This means that data retrieved from the regional databases are anonymous and cannot be traced back to identity individual patient in any way. For this reason, not even the informed consent of patients of Modena and Reggio Emilia hospitals will be collected.

Clinical data will be referred only for IRST patients to validate the algorithm. This is a non-interventional study based on secondary use of data collected for other purposes. So according to subparagraph 4 of Article 110-bis of the Privacy Code, which reports that " The processing of personal data collected for clinical purposes, for research purposes, by Scientific Institute for Research and Healthcare, public and private, does not constitute further processing by third parties because of the instrumental nature of health care activities carried out by these institutions compared to research, in compliance with the provisions of Article 89 of the Regulation" the IRCCS as IRST institute are exempt from collection of individual informed consent. Moreover, institutional informed consent form submitted to all patients at the first access in IRST included consent to use the patient's data, materials and/or test results for research purposes. In compliance with the "Code regarding the protection of personal data" (Legislative Decree 196/2003) appropriate safeguard will be implement to protect privacy.

### **6.2 Patient Data Protection**

IRST patient data retrieved from electronic health record will be used to validate algorithm Data will be anonymised and aggregated, stored in a computer database, maintaining confidentiality in accordance with national data legislation. For data verification purposes, authorized representatives of Sponsor/Promoter, a regulatory authority, an Ethics Committee may require direct access to parts of the hospital or practice records relevant to the analysis. The

responsible investigator will ensure that this project is conducted in agreement with either the Declaration of Helsinki (Tokyo, Venice, Hong Kong, Somerset West and Edinburgh amendments) or the laws and regulations of the country, whichever provides the greatest protection to the patient. The protocol has been written, and the project will be conducted according to the ICH Harmonized Tripartite Guideline for Good Clinical Practice (ref:<http://www.wma.net/en/30publications/10policies/b3/index.html>). The protocol will be approved by the Local, Regional or National Ethics Committees.

### **6.3 Source data**

For Reggio Emilia and Modena hospitals, patient information will be only retrieved from regional administrative health databases. Only for IRST patients data will be retrieved from electronic health records in order to validate algorithm.

The investigator is responsible for storage of essential documents before, during and after study completion, according to GCP (Good Clinical Practice). The Investigator must make study data accessible to the monitor, other authorized representatives of the Sponsor/Promoter (or designee), IEC, and Regulatory Agency inspectors upon request.

All study documents must be kept secured for a period of 15 years after completion or discontinuation of the study or for the length of time required by relevant national or local health authorities, whichever is longer. There may be other circumstances for which the Sponsor/Promoter is required to maintain study records and, therefore, the Sponsor/Promoter should be contacted prior to removing study records for any reason.

### **6.4 eCRF**

Not applicable.

#### **6.4.1 Paper CRF**

[figure not shown]
Not applicable.

#### **6.4.2 Study Database (applicable only for mono centric studies)**

Not applicable.

### **6.5 Laboratory examinations**

Not applicable.

## **6.6 Study Monitoring**

Principal Investigator agrees to perform the study in accordance with ICH Good Clinical Practice and to provide all information requested in the Study Database, in an accurate manner according to the instructions provided. The Investigator has responsibilities to the Health Authorities to take all reasonable steps to ensure the proper conduct of the study as regards ethics, protocol adherence, integrity and validity of the data recorded on the case report forms/study database.

If a monitoring visit is required the trial Monitor will contact the site to arrange a date for the proposed visit and will provide the site with written confirmation. Investigators will allow the trial staff access to source documents as requested.

The main duty of the Coordinating Center/Trial Monitor is to help the Investigator and the Study Coordinators to maintain a high level of ethical, scientific, technical and regulatory quality in all aspects of the study. According to the guidelines on ICH Good Clinical Practice, the trial monitoring aim is to check subject informed consent and the study database entries against the source documents. Trials staff will check data for compliance with the protocol, data consistency, missing data and timing. Investigator will be sent requests missing data or clarification of inconsistencies or discrepancies.

## **7. STATISTICAL CONSIDERATIONS**

### **7.1 Study design and objectives**

[figure not shown]
This is a multi-center, observational study involving retrospective collection of NSCLC patients information from regional administrative databases. All Patients identified through the algorithm as described at paragraph 4.1 will be considered.

Primary objective will be to measure a set of potential indicators (KPIs) derived from regional administrative database in order to investigate the appropriateness and quality of NSCLC care among participating sites.

The secondary aim will be to develop and validate an algorithm to identify the eligible population of the study from administrative databases against to a clinical database (only at IRST site).

### **7.2 Population size**

Due to the descriptive nature of the study without a hypothesis testing, a formal calculation of sample size and statistical power was not performed. Considering a preliminary analysis of clinical

medical charts from previous years in participating centers, it will be feasible to include about 400 patients with defined characteristics as defined at 4.1 paragraph.

[figure not shown]
### **7.3 Data analysis**

For primary objective, for each indicator, the proportion of patients who receive the procedure, in the defined time window, among those eligible will be calculated. Descriptive statistics as arithmetic mean and standard deviation (SD) as well as median value and minimum–maximum statistics will be presented for KPI related to average time. Two-sided 95% confidence interval (95% CI) will be reported as appropriate and specified for KPI expressed as proportion. For secondary objective, the validity of algorithm will be evaluated by individual matching among cases retrieved from administrative database and medical chart obtained from IRST. Following definition will be used to explain this objective: NSCLC cases appearing as incident cases in administrative database, but not in IRST clinical chart will be considered as false positive and those appearing in IRST clinical chart but not in administrative database will be considered as false negatives.

Sensitivity will be defined as the percentage of NSCLC cases correctly identified by the algorithm and calculated as the proportion among NSCLC cases identified both in administrative database and IRST clinical chart ('true positive' cases) and all cases identified as NSCLC cases from IRST clinical chart ('true positive' + 'false negative' cases). Positive predictive value will be defined as the percentage of NSCLC patients identified from IRST clinical chart were really NSCLC. This proportion will be calculated as the proportion among NSCLC cases identified both in administrative database and IRST clinical chart ('true positive' cases) and all cases identified as NSCLC cases from administrative database ('true positive' + 'false positive' cases).

Likewise, specificity and negative predictive value will be calculated, and exact (Clopper-Pearson) 95% confidence limits for binomial distribution will be applied.

Statistical analysis will be performed using Stata software 15.1/SE for Windows (Stata Corp LP, USA).

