##### **4.1 Definition of study groups**

An algorithm will be developed to reliably identify eligible subjects from administrative database SDO. The algorithm will apply specific criteria to patients collected in administrative databases from January 2017 to December 2017. It will be developed as the combination of ICD-9-CM codes with other criteria. Selection of codes and criteria was based on a discussion between senior Oncologists with expertise in lung cancer and the outcome research working group at IRST.

A first data extraction from the administrative database will be performed to identified potential study subjects. These data are related to patients with at least one hospitalization due to diagnosis of malignant tumors of trachea, bronchi and lungs between January and December 2017 using the International Classification of Diseases, 9th EDITION, (ICD-9-CM codes: 162\* in all position of diagnosis codes).

The following criteria will be applied to obtained patients, to exclude prevalence NSCLC cases (incident cases in 2014-2016 period), patients with mesothelioma (cod 163\*) and SCLC patients in order to obtain the correct population.

- Only NSCLC incident cases in 2017 will be considered, excluding prevalence cases that had the same diagnosis in the 3 years before the period of interest (2014-2016). Patients with at least one hospitalization due to diagnosis of malignant tumors of trachea, bronchi and lung according to ICD-9CM 162\* in the 3 years prior to the first index hospitalization on the year of evaluation (2017) will be excluded

- Patients with at least one hospitalization due to malignant tumor different than tumors of trachea, bronchi and lungs (ICD-9CM 140\*-161\* or 163\*- 195\* or 200\* - 208\* or V.10\* excluding V10.11 and V10.12), in the 3 years previous 2017 should be excluded.
- All patients with at least one ATC Code L01CB01
- Etoposide (VP-16) therapy administration in the 180 days following the first hospitalization index will be excluded.

After criteria application, the final population shall include only NSCLC patients.

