#### **4.2 Validation of algorithm (only at IRST site)**

Algorithm will be validated against the electronic medical record review. Validation will be performed applying the criteria described in 4.1 paragraph on electronic medical record of patients treated in IRST. The population obtained from administrative database and identified by the algorithm as NSCLC or non-NSCLC will be then compared with the corresponding cases identified in the medical chart, and performance of the algorithm will be evaluated. The corresponding medical chart of the selected sample cases will be consulted only for validation purposes. The definitions of algorithm will be subsequently revised to maximize the agreement and delete discrepancies with the patient medical chart to maximize the accuracy of the algorithm.

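### The validation reference does not consistently require NSCLC incident in 2017, so prevalent cases can be mis-scored and PPV for the incident population overstated

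*Protocol*

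**What the plan says.** Protocol section 4.1 sets the target: "Only NSCLC incident cases in 2017 will be considered, excluding prevalence cases that had the same diagnosis in the 3 years before" 2017. In discharge data this is done by excluding patients with at least one ICD-9-CM 162* hospitalisation in the three years before the index admission. The section then describes the result without mentioning incidence: "After criteria application, the final population shall include only NSCLC patients".

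Section 4.2 describes the validation at IRST in two ways. It says "Validation will be performed applying the criteria described in 4.1 paragraph on electronic medical record of patients treated in IRST". It also says that the patients "identified by the algorithm as NSCLC or non-NSCLC will be then compared with the corresponding cases identified in the medical chart". It adds that the algorithm will be revised afterwards to bring it into closest agreement with the chart.

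Section 7.3 gives the scoring rules:
- False positives: "NSCLC cases appearing as incident cases in administrative database, but not in IRST clinical chart will be considered as false positive".
- False negatives: "those appearing in IRST clinical chart but not in administrative database will be considered as false negatives".
- Sensitivity denominator: "all cases identified as NSCLC cases from IRST clinical chart ('true positive' + 'false negative' cases".
- PPV denominator: all NSCLC cases from the administrative database. The verbal description of PPV likewise concerns being NSCLC, not being newly diagnosed.

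Incidence appears once in these definitions, on the administrative side of the false-positive sentence. Nowhere does the protocol define a chart-positive case as first diagnosed in 2017, or say how a chart-confirmed prevalent case is scored.

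**The concern.** The secondary objective is to show that the algorithm finds the eligible population, and that population is incident. The accuracy formulas as written refer to a wider condition, NSCLC at any time. A validation whose reference condition differs from the selection target cannot show whether the incidence filter works.

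Three features of the plan make this matter:
- Section 4.2 revises the algorithm to agree with the chart, so the scoring rule shapes the final algorithm.
- Modena and Reggio Emilia supply only anonymised administrative data (sections 6.1 and 6.3), so IRST is the only site where prevalent cases slipping through can be detected.
- Such cases enter every KPI whose denominator is all patients identified by the algorithm (KPIs 2, 3, 7, 15 and 16), including KPI 2, metastatic disease at diagnosis.

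**Working it through.** The protocol states no accuracy target and no validation sample size, so there is no figure to reproduce. The only count is about 400 patients over three sites, a feasibility estimate (section 7.2).

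**How each kind of patient is scored**

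| Patient | Incident 2017 target | 7.3 formulas, literally | 4.1 look-back applied to the chart |
|---|---|---|---|
| Prevalent NSCLC, excluded by the algorithm | true negative | false negative | true negative |
| Prevalent NSCLC with no 162* admission in the previous 3 years (never admitted, or last admitted earlier), kept | false positive | true positive | true positive |

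The last column takes the look-back as section 4.1 words it, by earlier hospitalisation. The reference then applies the same test as the algorithm and cannot expose that test's misses.

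**Direction.** Let TP be incident cases kept, FP non-NSCLC cases kept, and p prevalent cases wrongly kept.
- PPV for incident NSCLC = TP/(TP + p + FP), which falls as p grows.
- PPV with p counted as true positives = (TP + p)/(TP + p + FP), which rises with p when FP > 0.
- Overstatement = p/(TP + p + FP).

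**Illustration.** All counts are assumptions: 133 incident cases at IRST (400/3), of which 120 are kept (about 90%); 30 non-NSCLC cases, of which 6 are kept (20%); 40 prevalent cases, of which 0, 4 or 12 are wrongly kept (0, 10 or 30%). For the last column, every prevalent case kept is assumed to pass the look-back in the chart too, and the 13 missed incident cases are assumed to remain chart-positive.

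| p | Incident target: sensitivity; PPV | 7.3 literally: sensitivity; PPV | Look-back on chart: sensitivity; PPV |
|---|---|---|---|
| 0 | 120/133 = 90.2%; 120/126 = 95.2% | 120/173 = 69.4%; 120/126 = 95.2% | 120/133 = 90.2%; 120/126 = 95.2% |
| 4 | 120/133 = 90.2%; 120/130 = 92.3% | 124/173 = 71.7%; 124/130 = 95.4% | 124/137 = 90.5%; 124/130 = 95.4% |
| 12 | 120/133 = 90.2%; 120/138 = 87.0% | 132/173 = 76.3%; 132/138 = 95.7% | 132/145 = 91.0%; 132/138 = 95.7% |

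At p = 4 the exact 95% limits for PPV are 86.3 to 96.2% (incident target) and 90.2 to 98.3% (p counted as true positives). Specificity and NPV are 60/70 = 85.7% and 60/73 = 82.2% for the incident target, against 24/30 = 80.0% and 24/73 = 32.9% for the literal formulas.

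**Sensitivity and the number of prevalent cases.** With p = 0, literal sensitivity is 120/(133 + P), where P is the number of prevalent cases in the charts. It is 82.2%, 69.4%, 60.0% and 45.1% for P = 13, 40, 67 and 133. Under the other two columns it stays at 90.2%.

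**The case against.** The strongest reply is that the protocol already carries incidence to the chart side.
- Section 4.2 applies the 4.1 criteria to the medical record, and section 7.4 speaks of applying the algorithm to both sources.
- The false-positive sentence can be completed as cases that do not appear as incident in the chart, with the false-negative clause taking the same sense.
- NSCLC in 4.2 and 7.3 may be shorthand for the population left after all the criteria.
- Section 4.1 first states the rule in terms of an earlier diagnosis, and nothing forbids a chart reviewer from using an earlier diagnosis found in the chart. Field-level abstraction rules often sit in an SAP or review manual, which is not at hand.

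Much of this stands. A reader might infer from 7.3 that the incidence filter is simply scored backwards and that the revision step must push the algorithm the wrong way. The documents do not support that as fact. It follows only from the literal formulas, and with the 4.1 criteria applied to the chart the false-negative error and the loss of sensitivity disappear. Nor does the protocol say that the chart's diagnosis date will be ignored, since it lists no chart fields.

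What does not stand is the conclusion that nothing needs changing. The look-back that section 4.1 spells out is an earlier hospitalisation. Applied to charts in that form, it leaves the PPV error in place. Even read as an earlier diagnosis within three years, it passes a patient diagnosed before 2014. Only the reading by the chart's own first-diagnosis date resolves the problem, and the protocol does not state it for the formulas. The numerators and denominators are fixed in the protocol itself, so this is not a detail left for later.

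**Conclusion.** The point holds as an inconsistent reference standard. Section 4.1 selects incident 2017 NSCLC, while section 4.2 and the 7.3 formulas are worded for NSCLC in general. The literal formulas mis-score prevalent patients in both directions. The 4.1 criteria applied to the chart as worded remove the false negatives but still count prevalent patients who escape the look-back as true positives, which overstates PPV for the incident population.

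The size is unknown. It depends on how many prevalent patients are in the IRST charts and how many pass the look-back, and the protocol gives neither. In the assumed setting with 40 prevalent cases, PPV is overstated by 4/130 = 3.1 points when 4 are wrongly kept and by 12/138 = 8.7 points when 12 are. The smaller figure lies within the width of the exact interval. The sensitivity loss applies to the literal reading only. The change should be made, because the validation steers the algorithm that the other two sites use without a check of their own.

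**What to change.** In sections 4.2 and 7.3, use one target condition:
- Reference-positive: chart-confirmed NSCLC with the first diagnosis date in the chart between 1 January and 31 December 2017, in a patient who meets the other eligibility criteria. This is determined from the chart, not from the 4.1 hospitalisation look-back.
- Reference-negative: every other reviewed patient, stating explicitly that chart-confirmed NSCLC first diagnosed before 2017 belongs here.
- Compute sensitivity, specificity, PPV and NPV on this basis, and replace the NSCLC or non-NSCLC comparison in 4.2 with it.

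Reporting false positives separately as not NSCLC and as NSCLC not incident in 2017 would be informative but is optional.

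The cost is a few lines of wording and one date read during a chart review that is already planned. PPV may come out less favourable.

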#### **7.4 Study duration**

For this retrospective study, duration will be strictly related to time used for algorithm development and application both for administrative database and IRST clinical chart, for revision of discrepancies and time for statistical analysis. This time will be estimated in about six months.

### **8. ETHICAL ASPECTS**

#### **8.1 Local regulations/Declaration of Helsinki**

[figure not shown]
The responsible Investigator will ensure that this study is conducted in compliance with the protocol, following the instructions and procedures described, adhering to the principles of Good Clinical Practice ICH Tripartite Guideline (December 2000) and in accordance with the principles laid down by the 18th World Medical Assembly (Helsinki, 1964 and further amendments) or with the laws and regulations of the country in which the research is conducted, whichever affords the greater protection to the individual.

#### **8.2 Independent Ethical Committee**

The protocol and any accompanying material provided to the patient will be submitted by the investigator to an Independent Ethical Committee for review. Approval from the committee must be obtained before starting the study. Any modifications made to the protocol, informed consent or material provided to the patient after receipt of the Ethics Committee approval must also be submitted by the investigator to the Committee in accordance with local procedures and regulatory requirements. The Independent Ethical Committee approval report must contain details of the trial (title, protocol number and version), documents evaluated (protocol, informed consent if required, accompanying material) and the date of the approval.

### **9. ADMINISTRATIVE REGULATIONS**

The group of Outcome Research is responsible for drawing up the final version of the protocol and implementing the algorithm, defining general organizational procedures and organizing periodic meetings and newsletters. The Outcome Research will also undertake the following: support for the preparation of all documents needed for EC submission of the study protocol for each participating center, training of staff assigned to data collection, definition of monitoring procedures.

The Outcome Research is responsible for sending (by mail) the specific study document to the Register of the Observational Studies (RSO) established by AIFA, with the aim of collecting, in a single national archive, the data related to non-interventional clinical research focused on drugs in a prospectively manner.

### **10.2 Curriculum vitae**

An updated copy of the curriculum vitae of each Principal Investigator, duly signed and dated, will be provided to the CC prior to the beginning of the study.

### **10.4 Insurance**

As this is an observational study, a specific insurance policy is not necessary in addition to the hospital insurance policy for daily clinical practice, according to “Determination AIFA 20 March 2008: Guidelines for the classification and conduction of observational study”.

[figure not shown]
